Effects of Reparel™ Knee Sleeve on Knee Osteoarthritis

Study Protocol & Statistical Analysis Plan

NCT04743921

April 4th, 2022

[name], Principal Investigator
University of Alabama at Birmingham
Birmingham, AL 35294

Objectives:

Osteoarthritis (OA) is one of the most prevalent musculoskeletal ailments worldwide. Numerous conservative therapies exist, but evidence for such treatments remains conflicting. Recently, there has been growing interest surrounding bioactive sleeves for managing knee arthritis. However, the literature on their efficacy for relieving pain and improving function in the setting of knee OA is limited. Therefore, we sought to investigate the effect of a bioactive sleeve on patient reported outcome measures (PROMs) in a small cohort of OA patients.

Methods:*Patient Recruitment and Inclusion*

Following institutional review board approval and registration with ClinicalTrials.gov, the authors will prospectively follow a series of patients at an outpatient orthopaedic sports medicine clinic between February and July 2021. Patients who opt for non-operative management of knee OA will be informed and consented for the study. Patients will be included if they have radiographic evidence of knee OA, no previous surgery on the symptomatic knee, no corticosteroid knee injection within 3 months of the study, and agree to abstain from a knee injection during the 3 month study period. Patients will be excluded if diagnosed with bilateral symptomatic knee OA, had previously undergone knee surgery, were grossly unstable on physical examination, or had a history of knee malignancy. Patients will be instructed to wear the sleeve (Reparel, Chico, CA) as long as tolerated throughout the day and to refrain from modifying usual activities and diet.

Patient Assessment

Participants will be asked to complete the following patient reported outcome measures (PROM): the University of California, Los Angeles Activity Score(UCLA),¹¹ which measures current activity level; the Lysholm Score(LKS),¹² which measures joint stability and function; the Oxford Knee Score (OKS),¹³ which measures knee related health status; the Knee Injury and Osteoarthritis Outcome Score (KOOS),¹⁴ which assesses difficulties with physical activity; the Single Assessment Numeric Evaluation (SANE),¹⁵ which assesses perceived functional level; and the Visual Analog Scale (VAS),¹⁶ which assesses perceived pain level. These surveys will be administered at the initial visit and subsequently over the phone at 2 weeks, 6 weeks, and 3 months later. Patients will also be asked about average daily sleeve usage, product satisfaction, and complaints/issues.

Osteoarthritis Severity Assessment

OA severity will be defined by clinical radiographic imaging using the Kellgren-Lawrence (KL) classification system at the baseline clinical visit.¹⁷ The radiographs will be read and graded by a sports medicine fellowship trained orthopedic surgeon.

Statistical Analysis

Statistical analysis will be performed using SPSS (IBM SPSS Statistics for Macintosh, Version 27.0. Armonk, NY: IBM Corp). Mann-Whitney test will be used to compare baseline demographics between male and female patients. Wilcoxon Signed-Rank test will be used to compare baseline PROMs and hours of sleeve use with those at 2 week, 6 week, and 3 month time points. Kruskal Wallis test will be performed to evaluate differences in PROs between the four time points. When analyzing PROs between

time points within groups with differing population counts, only patient scores that are available between groups will be analyzed. Significance will be set to an alpha of 0.05.

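### The title and objective name the effect of the sleeve, but every planned analysis of the outcome scores tests change over time without a comparator, so p<0.05 cannot be attributed to the sleeve

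*Combined protocol and SAP*

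**What the plan says.** The title of the combined protocol and SAP is "Effects of Reparel™ Knee Sleeve on Knee Osteoarthritis". The Objectives section gives the aim as "we sought to investigate the effect of a bioactive sleeve", with PROMs as the outcome and a small cohort as the setting.

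Under Patient Recruitment and Inclusion, the design is to "prospectively follow a series of patients" at one outpatient clinic. On entry: "Patients who opt for non-operative management of knee OA will be informed and consented for the study". On treatment: "Patients will be instructed to wear the sleeve (Reparel, Chico, CA) as long as tolerated throughout the day". No sham, untreated, historical or external comparator is described, nor a run-in or pre-sleeve trend. Patients agree to have no knee injection for the 3 months and are asked to keep activity and diet unchanged. Analgesics and physiotherapy are not mentioned.

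Under Patient Assessment, six self-reported instruments are completed at the initial visit, then by phone at 2 weeks, 6 weeks and 3 months.

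Under Statistical Analysis: "Wilcoxon Signed-Rank test will be used to compare baseline PROMs" with each later time point, and a Kruskal-Wallis test compares the four time points. The other listed tests are a Wilcoxon test on hours of use and a Mann-Whitney test of baseline demographics by sex. Alpha is 0.05. Nothing says how a significant change is to be interpreted.

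**The concern.** The quantity named in the title and objective is causal: what the sleeve does to the scores. The quantity tested is different: whether scores after baseline differ from baseline in people who all received the sleeve. The 5% error rate belongs to the hypothesis of no change over time. It gives no protection against wrongly concluding that the sleeve works.

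Several features of this plan could produce change with an inert sleeve:

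- Patients enter when attending a clinic with a symptomatic knee, so baseline may be worse than their usual state.
- They know that they are wearing the device, and every PROM is self-reported.
- Care other than injections, activity and diet is not addressed.
- Scores move from initial-visit to phone collection just as the sleeve is introduced.

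Without a stated limit on interpretation, a significant improvement could easily be reported as an answer to the causal objective.

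**Working it through.** **Structural check.** The plan has no sample size, power, effect size or SD, so there is no figure of its own to reproduce. Setting each planned test beside what it compares:

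| Planned test | What is compared | Treatment contrast? |
|---|---|---|
| Wilcoxon signed-rank, PROMs | baseline v. 2 weeks, 6 weeks, 3 months | no; time only |
| Kruskal-Wallis, PROMs | four time points | no; time only |
| Wilcoxon signed-rank, hours of use | time points | no |
| Mann-Whitney | baseline demographics, male v. female | no |

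No test has the null hypothesis of no sleeve effect. The limits on injections, activity and diet remove some rival explanations but do not create a comparator.

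**Illustration of size.** Only alpha = 0.05 comes from the documents. They do not state sidedness; two-sided is assumed. The other inputs are also assumptions: true sleeve effect zero; n = 20, 30 or 50; test-retest correlation r = 0.6 to 0.8; baseline on average z SD worse than the patients' own usual level; normal scores with equal variance at both times.

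- Expected improvement from regression to the mean: (1 − r)z, in SD of the score.
- SD of the change: √(2(1 − r)).
- Standardised shift seen by the test: the first divided by the second.

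Examples:

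- r = 0.7, z = 1: improvement 0.3 × 1 = 0.30; SD of change √0.6 = 0.775; shift 0.30/0.775 = 0.39.
- r = 0.7, z = 0.5: improvement 0.15; shift 0.15/0.775 = 0.19.
- Mildest cell with z of 0.5 to 1 (r = 0.8, z = 0.5): 0.10/√0.4 = 0.10/0.632 = 0.16.
- Strongest (r = 0.6, z = 1): 0.40/√0.8 = 0.40/0.894 = 0.45.

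Simulating the Wilcoxon test with these shifts (3,000 runs per cell; repeat runs differ by up to about 2 percentage points):

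| z | r | n | Trials significant with an inert sleeve |
|---|---|---|---|
| 0 | 0.6-0.8 | 20-50 | about 5% |
| 0.25 | 0.6-0.8 | 20-50 | about 5-12% |
| 0.5 | 0.7 | 20 / 30 / 50 | about 12% / 17% / 27% |
| 1 | 0.7 | 20 / 30 / 50 | about 36% / 53% / 75% |
| 0.5-1 | 0.6-0.8 | 20-50 | about 9-86% |

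**Cross-check with another selection model.** Suppose patients do not present in the mildest 30% to 50% of states, with correlation 0.5 to 0.8. Regression to the mean alone then gives 10-43% at n = 20, 14-63% at n = 30 and 19-84% at n = 50 (4,000 runs per cell).

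**Other sources.** Placebo response, natural course or other care act in the same way. A mean improvement of 0.3 SD of the change score from any of these gives significance in 24%, 35% and 53% of trials at n = 20, 30 and 50.

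**The case against.** The strongest reply is that the plan hides nothing. It describes a followed series in a small cohort, and its aim is to investigate an effect, not to assert one. It contains no success criterion, superiority hypothesis or attribution rule. This stands. A reader might infer that the plan declares any significant change to be proof that the sleeve works; the text does not say so. The fault is a mismatch between causal wording and an uncontrolled design, together with silence on interpretation.

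The percentages are also open to challenge, and rightly. The formula (1 − r)z applies when patients enter during a transient bad spell. The eligibility criteria set no pain or function threshold. Entry turns on radiographic OA, surgical and injection history, and the choice of non-operative care. If clinic patients are worse than others because their disease is stably more severe, that part does not regress, and the error rate from this source stays near 5% however severe they are. A reader might take 9-86% as the false-positive rate of this trial; the documents do not support that, since they give no sample size, correlation or degree of selection.

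The structural point survives both replies. Even with no regression to the mean, the other explanations remain and no planned test can exclude them.

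It is also tempting to relate change to hours of use and read a dose-response as support. Wear time is self-chosen and self-reported, so it may follow symptoms or perceived benefit. That analysis would invite the causal reading which the design cannot bear.

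**Conclusion.** The concern holds as a mismatch between the named target and what is tested. From the documents alone, p<0.05 on any PROM would show change from baseline and could not be assigned to the sleeve. That conclusion needs no numerical assumption.

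Its size in this trial is unknown. Under the assumed inputs, an inert sleeve gives a significant result anywhere from the nominal 5% (no transient bad spell) to 86% (baseline 1 SD worse than usual, r = 0.6, n = 50). These figures show that the problem can be large; they do not estimate it.

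The planned tests can still be run as tests of change. What must alter is the stated target and the interpretation.

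**What to change.** 1. Restate both the title and the objective as estimating within-patient change in PROMs over 3 months of sleeve use. Add a sentence under Statistical Analysis that a significant change will not be reported as an effect of the sleeve.
2. For each PROM, report the paired median change (Hodges-Lehmann estimate) with its 95% CI beside the Wilcoxon p-value, labelled as uncontrolled change.

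This needs no new patients or data, only wording and a small amount of extra analysis. The price is a weaker claim. A concurrent comparator, ideally a sham, would be needed to keep the causal objective. That would be a different trial, and the documents give no SD or target difference from which to size it. The document is dated April 2022 and the stated clinic period is February to July 2021, so wording and reporting are the practical place to act.

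### The pre-study washout covers only corticosteroid knee injections, so the effect of another recent injection could enter the uncontrolled change from baseline (minor; size unknown, possibly zero)

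*Combined protocol and SAP*

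**What the plan says.** Under Patient Recruitment and Inclusion, two inclusion criteria deal with injections:

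- Before the study: "no corticosteroid knee injection within 3 months of the study".
- During the study: patients must "agree to abstain from a knee injection during the 3 month study period".

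The first is limited to one drug class; the second is not. The exclusion list ("Patients will be excluded if diagnosed with bilateral symptomatic knee OA, had previously undergone knee surgery, were grossly unstable on physical examination", and knee malignancy) does not mention injections.

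The design is a single cohort: "the authors will prospectively follow a series of patients at an outpatient orthopaedic sports medicine clinic". Under Statistical Analysis, "Wilcoxon Signed-Rank test will be used to compare baseline PROMs and hours of sleeve use with those at 2 week" and at the two later time points. No comparison group is described, and no adjustment, stratification or sensitivity analysis for earlier injections. The Patient Assessment section lists the questionnaires and some questions on sleeve use, satisfaction and complaints, but nothing on injection history.

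**The concern.** By barring injections of any kind during follow-up, the protocol treats them as able to disturb the outcome scores. The same reasoning applies to an injection given shortly before baseline, but there the protocol screens out one class only.

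In a randomised trial, earlier treatment would be balanced on average between arms. Here each patient's own baseline is the only comparator. If an injection's effect is still building at baseline, later scores improve for a reason unrelated to the sleeve. If it is wearing off, later scores worsen and can hide a real benefit. The Objectives describe the study population as a small cohort, so a few such patients could matter.

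**Working it through.** **Nothing to reproduce.** The document gives no sample size, power, effect size or standard deviation. The check is a reading of the criteria followed by an illustration.

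**Step 1: the criteria side by side.**

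| Period | Corticosteroid injection | Other knee injection |
|---|---|---|
| 3 months before | not allowed | not mentioned |
| 3 months during | not allowed | not allowed |

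No exclusion criterion fills the open cell, so the gap in eligibility is in the text.

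**Step 2: inputs for the illustration.** From the document: alpha 0.05, and the Wilcoxon signed-rank test against baseline. All else is assumed:

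- two-sided testing (the plan does not state sidedness), one outcome at one time point;
- n = 20, 30 or 50;
- correlation 0.7 between baseline and follow-up, so the SD of change is sqrt(2 × (1 − 0.7)) = 0.775 baseline SD;
- share of patients affected: 5%, 10% or 20%;
- change in score caused by the injection during follow-up: 0.2, 0.5 or 0.8 baseline SD;
- normally distributed changes.

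**Step 3: shift in the mean change.**

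shift = share × effect × (proportion building − proportion waning)

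- All building, smallest case at a 10% share: 0.10 × 0.2 = 0.02 SD.
- All building, 0.5 SD: 0.10 × 0.5 = 0.05 SD and 0.20 × 0.5 = 0.10 SD.
- All building, largest case: 0.20 × 0.8 = 0.16 SD.
- 75% building and 25% waning: multiply by 0.75 − 0.25 = 0.5.
- Even mix, or no affected patients: 0.

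**Step 4: rejection rate with an inert sleeve and no other source of change** (simulation; the last digit carries simulation error; ranges run over n = 20 to 50 and the shares shown).

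| Direction | Effect | Share | Rejection |
|---|---|---|---|
| none affected | – | 0 | 4.9–5.0% |
| all building | 0.5 SD | 5% | 5.0–5.5% |
| all building | 0.2 SD | 10–20% | 5.0–6.3% |
| all building | 0.5 SD | 10–20% | 5.4–13.2% |
| all building | 0.8 SD | 10–20% | 6.5–23.7% |
| 75/25 mix | 0.5 SD | 10% | up to about 5.5% |
| 75/25 mix | 0.5 SD | 20% | 5.6–7.0% |
| even mix | 0.5 SD | 5–20% | 4.8–5.0% |

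**Step 5: the opposite direction.** Suppose the sleeve truly adds 0.3 SD (assumed) and every affected patient wanes by 0.5 SD. For n = 20/30/50, power falls from 35.6/51.6/74.6% with nobody affected to 26.0/37.8/57.6% at a 10% share and 17.9/25.8/39.9% at 20%.

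**Step 6: comparison with the single-arm problem.** A 0.3 SD improvement from natural course, placebo response or regression to the mean, with an inert sleeve and no injected patients, shifts the changes exactly as a 0.3 SD sleeve effect would. The test then rejects in 36/52/75% of studies at n = 20/30/50, more than in any setting in Step 4 at the same n.

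**The case against.** The strongest reply is that the document shows an asymmetry of wording and not a bias. Nothing in it says that the clinic gives other injections, that any enrolled patient had one, or that such an effect changes over three months. The larger rejection rates need a high share, a large effect and a single direction all at once; small or mixed effects leave the test close to nominal. The single-arm design does more harm than this gap could, and the plan also leaves other co-treatments, such as oral analgesics, unrestricted. The three-month window is chosen for corticosteroids, and nothing shows that it suits other products.

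Most of this stands, and it limits the point to a minor one. It does not close the gap: the criterion admits these patients, and closing it is cheap. That a larger problem exists is no reason to leave a smaller, separable one in place. The window is at least the protocol's own, and a look-back that records dates would allow another to be examined.

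A reader might go further and infer that carry-over did bias the result, or that it favours the sleeve. The documents support neither: enrolment of such patients is unknown, and waning would work against the sleeve. Nor does the absence of injection history from the Patient Assessment section show that it is unavailable. That section is not a full data inventory, and clinic records may hold the information.

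**Conclusion.** The gap in the eligibility wording is real, and its effect is unknown. A non-corticosteroid knee injection shortly before baseline does not bar entry, and with no comparator a changing effect of that injection could add to or subtract from the tested change. Share, effect size, direction, correlation and n are all assumptions. Across 10–20% shares with every affected patient building, the rejection rate under an inert sleeve runs from nominal (5.0%) to 23.7%. It is near nominal at a 5% share with effects up to 0.5 SD, and uninflated under an even mix. These rates isolate the injection effect; without a control arm the actual rate under an inert sleeve need not be 5% in any case. Severity is minor.

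**What to change.** The document is dated "April 4th, 2022" and places the study "at an outpatient orthopaedic sports medicine clinic between February and July 2021", so enrolment is probably complete. In that case:

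1. From clinic records or the patients, obtain the type and date of every knee injection in the 3 months before baseline, and report how many patients had one. If none did, the point is closed.
2. If some did, keep the full cohort as the main analysis and repeat the comparisons of baseline with 2 weeks, 6 weeks and 3 months without those patients. Compare the median changes and not only the p-values, since a smaller sample alone weakens a p-value.

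If any enrolment remains, widen the pre-study criterion to injections of any type into the knee, with the same 3-month window.

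The cost is one look-back and one sensitivity analysis, or one clause of wording, and perhaps a few patients. For an assumed true effect of 0.3 SD, power at n = 20/30/50 is 35.6/51.6/74.6%. Removing 10% of patients (n = 18/27/45) gives 32.4/47.0/69.8%; removing 20% (n = 16/24/40) gives 30.1/42.5/64.5%. If the main analysis keeps everyone, that loss falls only on the sensitivity analysis. None of this replaces a control arm: regression to the mean, placebo response and natural course remain.

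### Baseline PROMs are taken at the clinic visit and every follow-up by phone, so all 18 baseline comparisons would count any visit-to-phone difference in answers as change on the sleeve.

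*Combined protocol and SAP*

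**What the plan says.** Patient Assessment lists six instruments (UCLA, Lysholm, OKS, KOOS, SANE and VAS) and sets their timing and setting: "These surveys will be administered at the initial visit and subsequently over the phone at 2 weeks, 6 weeks, and 3 months later". The first contact is in clinic: the section on osteoarthritis severity grades radiographs "using the Kellgren-Lawrence (KL) classification system at the baseline clinical visit", and recruitment is at an outpatient clinic.

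On how the forms are filled in, the text uses two verbs. It says "Participants will be asked to complete the following patient reported outcome measures (PROM", and then that the surveys are administered. The list ends with "and the Visual Analog Scale (VAS", a scale with a visual format, and no telephone version is described.

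Statistical Analysis plans two analyses of these scores over time: "Wilcoxon Signed-Rank test will be used to compare baseline PROMs and hours of sleeve use with those at 2 week", continuing to 6 weeks and 3 months, and "Kruskal Wallis test will be performed to evaluate differences in PROs between the four time points". The Methods describe one series of patients and no comparator. The Objectives give the aim: "we sought to investigate the effect of a bioactive sleeve on patient reported outcome measures (PROMs) in a small cohort of OA patients".

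Nothing in the document provides for matched administration, an adjustment for setting, or a sensitivity analysis for it.

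**The concern.** The only pre-sleeve scores come from the visit and the only on-sleeve scores come from the phone. Setting and sleeve exposure change together in every patient, so no baseline comparison can separate them. If people answer differently in clinic than on the telephone, or on a form than to an interviewer, that difference goes straight into the estimated change.

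With matched collection, this design could at least estimate change from baseline free of this particular bias. As planned, even that estimate may be off, possibly by a different amount for each PROM. Two things that usually reassure would not help here. Consistent results at 2 weeks, 6 weeks and 3 months share the same visit baseline and the same phone setting. A larger sample only narrows the interval around the shifted value.

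**Working it through.** The plan states no sample size, SD, power or expected change, so it has no figure of its own to reproduce.

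**1. Count, from the document.** Six PROMs × three follow-ups = 18 signed-rank comparisons with baseline. Baseline is always the visit and follow-up is always the phone, so 18 of 18 cross the change of setting. The document does not print this count; it assumes one score per instrument. If KOOS were scored as five subscales (an assumption), the count would be (5 + 5) × 3 = 30, and all 30 would still cross. Comparisons of hours of sleeve use are not included. The Kruskal-Wallis test has one visit time point and three phone time points.

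**2. How a shift enters.** Let μ be the true mean change and δ a constant visit-to-phone shift. The observed mean follow-up minus baseline is then μ + δ, whatever the sample size. The difference between two phone contacts contains δ − δ = 0.

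**3. Illustration of size.** Everything in this step is assumed: n = 20 to 50, correlation between contacts r = 0.6 or 0.8, normal scores with SD 1, and the same δ for all patients and all phone contacts.

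- SD of a paired difference = √(2(1 − r)): √0.8 = 0.894 for r = 0.6, and √0.4 = 0.632 for r = 0.8.
- Noncentrality = δ√n / SD of the difference. For n = 30 and δ = 0.2: 0.2 × 5.477 / 0.894 = 1.225, and 0.2 × 5.477 / 0.632 = 1.732.
- Coverage of μ by a nominal 95% paired t interval = probability that a noncentral t with n − 1 degrees of freedom lies between ± the critical value (2.045 for n = 30). It does not depend on μ or on the sign of δ.

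| Assumed shift δ | n = 20, r = 0.6 / 0.8 | n = 30, r = 0.6 / 0.8 | n = 50, r = 0.6 / 0.8 |
|---|---|---|---|
| 0.05 SD | 0.944 / 0.937 | 0.940 / 0.930 | 0.933 / 0.915 |
| 0.1 SD | 0.924 / 0.897 | 0.909 / 0.867 | 0.879 / 0.805 |
| 0.2 SD | 0.842 / 0.731 | 0.780 / 0.612 | 0.659 / 0.408 |

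The t interval is used here because it has a closed form. The planned test is the signed-rank test, so it was simulated under the same assumptions with no true change:

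- The shift that doubles the 5% error rate of one two-sided test to 10% is 0.148 / 0.101 SD at n = 20, 0.114 / 0.081 SD at n = 30 and 0.089 / 0.062 SD at n = 50 (r = 0.6 / 0.8).
- At n = 30, the chance that all three follow-ups are significant for one PROM is about 0.3% with no shift, and 4.9% / 14.0% at 0.2 SD.
- Phone-to-phone tests stay at about 5% whatever the shift.

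**The case against.** The strongest reply is that no difference in mode has been shown. The surveys are said to be administered at both kinds of contact. If staff read them out each time, only the setting differs, and the effect could be negligible. This stands: the documents establish a change of setting, not a change in answers. The supported statement is that the plan may bias the change from baseline. A reader might infer that phone follow-up flatters the sleeve, or that the results are invalid for this reason. The documents support neither, because they give no size and no direction.

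Second, the illustration depends wholly on assumed values and runs from trivial to severe. This also stands. The only figure drawn from the document is 18 of 18; the percentages cannot be used to grade this trial.

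Third, the missing control group already prevents attributing change to the sleeve, since natural course, regression to the mean and expectation sit in the same 18 comparisons. That is correct and makes this point secondary. Wording the conclusion as change from baseline, rather than as an effect of the sleeve, answers the missing control group and would be needed even with matched collection. A reader might also infer that matching the mode would let the study estimate the sleeve's effect; it would not. What matching protects is the change from baseline itself, and that is worth protecting at low cost.

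Fourth, the series was planned for February to July 2021 and the document is dated April 2022, so a change to collection may have no one left to apply to. That is likely, and it is why reporting steps are also given below.

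**Conclusion.** The point holds as a possible, avoidable bias of unknown size and direction. All 18 baseline comparisons, with one score per instrument, cross from visit to phone, and no planned analysis can detect or remove a difference in answers. Whether it matters depends on facts the documents leave out: whether visit forms are self-completed or read out, and how the VAS is obtained by phone. Under the assumed conditions a shift of 0.05 SD hardly matters and one of 0.2 SD does; the documents cannot say which applies, or whether there is any shift at all. It should be addressed because the remedy is cheap, but it ranks below the lack of a comparator.

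**What to change.** **For any patients still to be enrolled** (none are described after July 2021): collect the pre-sleeve baseline with the same instrument format and wording as follow-up. Use either one self-completed electronic form at all four contacts, or one scripted interview at all four with a pain rating that can be given by phone. Reading the script at the visit matches wording and format, though not setting. The cost is a short scripted baseline interview or a changed pain-scale format, with no extra patients or procedures.

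**For data already collected:**

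1. Report how each PROM, including the VAS, was obtained at each contact.
2. Give each change from baseline as a Hodges-Lehmann estimate with a 95% CI obtained by inverting the signed-rank test, so that interval and planned test agree.
3. Where a result is significant, state beside the CI that a visit-to-phone shift in the direction of the observed change, as large as the limit nearer zero, would be enough to remove significance.
4. The phone-to-phone change from 2 weeks to 3 months may be shown as descriptive only. It is free of the change of setting but has no pre-sleeve value, so it cannot estimate an effect of the sleeve.

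The cost is a few sentences and intervals computed from existing data. None of this replaces a control group.

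### The PROM analysis is rank tests at alpha 0.05 with no estimate of change or interval, so a small change could be read as benefit and a worthwhile one as no effect

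*Combined protocol and SAP*

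**What the plan says.** The Objectives section gives the aim as investigating the sleeve's effect on "patient reported outcome measures (PROMs) in a small cohort of OA patients". The background sentence before it notes that "the literature on their efficacy for relieving pain and improving function in the setting of knee OA is limited".

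Under Patient Assessment, six instruments are listed: UCLA, Lysholm, OKS, KOOS, SANE and VAS. Each is described only by what it measures, for example "the Visual Analog Scale (VAS),¹⁶ which assesses perceived pain level". They are "administered at the initial visit and subsequently over the phone at 2 weeks, 6 weeks, and 3 months later".

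The Statistical Analysis section contains two analyses of these scores:

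- Baseline against each follow-up: "Wilcoxon Signed-Rank test will be used to compare baseline PROMs and hours of sleeve use with those at 2 week, 6 week, and 3 month".
- All visits together: "Kruskal Wallis test will be performed to evaluate differences in PROs between the four time points".

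The only other test concerns baseline characteristics, not PROMs: "Mann-Whitney test will be used to compare baseline demographics between male and female patients". The only numerical criterion is this: "Significance will be set to an alpha of 0.05". Neither the protocol text nor the analysis section names a paired change estimate, a confidence interval, a meaningful-change threshold or a responder definition for any scale.

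**The concern.** The aim is to learn what the sleeve does to patient-reported scores. The planned output is a set of p-values. A signed-rank p-value gives evidence that the paired differences are not centred on zero. It does not say how large the change was or how precisely it was measured. It depends on the number of pairs and on the spread of the differences as well as on the size of the change, so the same p-value can accompany a minor or a substantial improvement.

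Two misreadings become possible. If enough pairs are available, a change too small for patients to notice could be taken as benefit. If few are available, a change that patients would value could fail to reach 0.05 and be taken as absence of effect. An estimate with its interval guards against both, and the plan provides neither.

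**Working it through.** **Figures in the documents.** Alpha 0.05, six instruments, three follow-ups (2 weeks, 6 weeks, 3 months) and a cohort described as small. There is no sample size, SD, target difference or power, so there is no planned figure to reproduce.

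**Assumptions, none of them in the documents.** Two-sided test; VAS scored 0-10; normally distributed paired changes with SD 2.0 to 2.5 points; 10 to 60 complete pairs.

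**Step 1: smallest mean change that just reaches p<0.05.** With the signed-rank test's large-sample efficiency of 3/π = 0.955 relative to the paired t-test:

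change = 1.96 × SD / √(0.955 × n)

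| Pairs | √(0.955n) | SD 2.0 | SD 2.5 |
|---|---|---|---|
| 10 | 3.09 | 1.27 | 1.59 |
| 20 | 4.37 | 0.90 | 1.12 |
| 40 | 6.18 | 0.63 | 0.79 |
| 60 | 7.57 | 0.52 | 0.65 |

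The formula is approximate, most of all at n = 10.

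**Step 2: where this falls to 1 point.** Solving for n gives n = (1.96 × SD)² / 0.955.

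- SD 2.0: 3.92² / 0.955 = 15.37 / 0.955 ≈ 16.
- SD 2.5: 4.90² / 0.955 = 24.01 / 0.955 ≈ 25.

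One point is used only as a marker on the scale, not as an established threshold. Below about 16 to 25 pairs, a significant result needs an observed change above 1 point. Above that, a change below 1 point can be significant.

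**Step 3: how often a given true change reaches p<0.05.** Simulated signed-rank tests, over the same SD range:

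- True change 0.8 points: about 14-20% of trials with 10 pairs, 26-38% with 20 and 67-85% with 60.
- True change 1.5 points: about 38-54% with 10 pairs.
- True change of half an SD (1.0 point at SD 2.0, 1.25 at SD 2.5): about 29% with 10 pairs, 54% with 20 and 73% with 30.

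With 10 pairs, a 1.5-point improvement is therefore missed in roughly half of trials. With 60 pairs, a 0.8-point improvement is significant in most. The p-value alone does not tell a reader which situation applies.

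**Step 4: can responder counts stand on their own?** The share of patients improving by more than c points when the true mean change is zero is 1 − Φ(c/SD).

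- c = 1: 1 − Φ(0.50) = 31% (SD 2.0); 1 − Φ(0.40) = 34% (SD 2.5).
- c = 2: 1 − Φ(1.00) = 16% (SD 2.0); 1 − Φ(0.80) = 21% (SD 2.5).

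Without a control group, these patients cannot be told apart from true responders. A responder percentage is therefore useful description but weak evidence of benefit.

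**The case against.** The strongest reply is that the plan states no success criterion. It sets a test and an alpha and gives no rule for announcing relief of pain or better function. A reader might infer that a trivial change would be reported as relief. The documents do not support that: they leave the wording of conclusions open, and being silent about medians or changes does not forbid reporting them. This stands, and the consequence is only that a misreading could happen. It does not remove the gap, because an unwritten intention to report estimates does not commit anyone to doing so.

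Second, the sentence about relieving pain and improving function describes the literature. The stated aim is exploratory, concerns effects on PROMs, and is pursued in an uncontrolled series. This also stands. It weakens any case for a formal claim rule, but an exploratory series depends on estimates at least as much as a confirmatory trial does.

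Third, every input to the illustration is assumed. A reader might pick out the larger sample sizes and conclude that overstating trivial change is the main danger. The only size information points the other way: in a small cohort, missing a worthwhile change is at least as likely.

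Fourth, the document is dated April 4th, 2022, while patients were to be followed between February and July 2021. Thresholds may no longer be fixable before analysis. That limits what responder figures can be called. It does not affect change estimates and intervals, which need no threshold.

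**Conclusion.** The point holds in this form: the PROM analysis consists only of rank tests at alpha 0.05, with no estimate of the size of change and no interval. Followed as written, it can show that scores moved but not by how much, which falls short of the stated aim.

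The absence of an estimate and an interval is plain from the text and rests on no assumption. The size of the consequence does rest on assumptions. The illustrative figures depend on an assumed 0-10 VAS, SD of change 2.0-2.5, a two-sided test and an unknown number of pairs, and they do not carry over to the other five instruments. What does carry over is that significance alone does not fix the size of the change. The error could go either way, and nothing in the documents shows that either has occurred.

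This is a change that should be made because it is cheap and improves the answer. The planned tests can still be run without it.

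**What to change.** In Statistical Analysis, state that for each PROM at each follow-up the paired change from baseline will be reported as a Hodges-Lehmann estimate with a 95% confidence interval, beside the Wilcoxon p-value. State also that conclusions will rest on the estimate and its interval rather than on p alone. With six instruments and three follow-ups this is 6 × 3 = 18 estimates if each instrument gives one score.

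As secondary, descriptive output, report the proportion of patients, with an exact 95% confidence interval, who reach a cited meaningful-change threshold for each scale. Label it uncontrolled, because some patients cross any threshold with no true mean change. Label it post hoc if the threshold is chosen after analysis has begun. The documents give no threshold values, and none is proposed here.

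I would not make a claim conditional on reaching both a threshold and p<0.05. That would still bar a large but non-significant change in a small cohort. It would also apply a patient-level threshold to a group-level estimate, and so could hide a real improvement confined to a minority.

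The cost is a few lines of text and minor extra output from data already collected. Some results may be described less favourably, and published thresholds vary between sources, so the one used must be cited. The change does not supply a control group: the estimates will describe change during sleeve use, not change caused by the sleeve.
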